16.8 Pregnancy Test

Pregnancy test results will be listed for patients with any positive results.

16.9 Events of Death

Events of deaths will be summarized by treatment group, reason of death and study period . In addition, events of death will be listed.

Time-to-death will be investigated graphically using a Kaplan Meier plot and modelled, if applicable, by applying a Cox proportional-hazards model incl. treatment group, CCl and region as covariates. For patients with no unique date-of-death the date of the last completed visit will be used. Patients still alive at the time of the safety follow-up visit will be censored using the date of the last safety follow-up visit as last observed time point.

17 Pharmacokinetic/Pharmacodynamic Analysis

The population pharmacokinetics of Lu AF82422 will be determined by means of non-linear mixed effect analysis. Estimated parameters of plasma exposure per patient (e.g. AUC and Cav) will be related to the efficacy and safety/tolerability in an exploratory PK/PD analysis. Details of the popPK and PK/PD analyses will be given in a separate popPK/PD analysis plan. The results of the popPK and PK/PD analyses will be reported in a popPK/PD report and relevant parts of it might be given in the clinical study report.

18 Immunogenicity Analysis (ADA)

The analysis of anti-Lu AF82422 antibodies will be performed for all subjects in the APTS receiving at least one dose of Lu AF82422. Subjects receiving placebo will not be analyzed for anti-Lu AF82422 antibodies.

Pre-existing ADA	Refers to antibodies reactive with the biologic drug that are present in subjects be- fore drug administration
Treatment-induced ADA	ADA developed de novo following drug administration
Treatment-boosted ADA	Pre-existing ADA that were boosted to a higher-level following drug administra- tion, i.e., titer is greater than the baseline titer by a fourfold increase
Neutralizing ADA (NAb)	ADA that inhibits or reduces the pharmacological activity of the drug
ADA-positive subject	A subject with at least one treatment-induced or treatment-boosted ADA-positive sample at any time during the treatment or follow-up observation period
ADA-negative subject	A subject without a treatment-induced or treatment-boosted ADA-positive sample during the treatment or follow-up observation period
ADA-inconclusive subject	A subject who cannot irrefutably be classified as ADA-negative since drug is present in the same sample at a level exceeding the validated drug tolerance level, i.e., drug tolerance
Transient ADA	ADA detected only at one sampling time point during the treatment or follow-up observation period, or ADA detected at two or more sampling time points during the treatment separated by a period less than 16 weeks, and the subject's last sampling time point is ADA-negative
Persistent ADA	Treatment-induced ADA detected at two or more sampling time points during the treatment (including safety follow-up period) where the first and last ADA-positive samples are separated by a period of 16 weeks or longer, or ADA incidence only in the last sampling time point of the treatment study period or at a sampling time point with less than 16 weeks before an ADA-negative last sample
Onset of ADA	Onset defined as the time period between the initial administration of IMP and the first instance of treatment-induced ADA
Duration of ADA	Referring to the longevity of treatment-induced ADA
ADA prevalence	The proportion of subjects having anti-drug antibodies (including pre-existing antibodies) at any point in time
ADA incidence	The proportion of subjects found to have seroconverted or boosted their pre- existing ADA during the study period

Panel 4 ADA definitions

Study 18331A - Statistical Analysis Plan

The following analysis will be carried out to the extent meaningful based on the total number of subjects identified with pre-existing or treatment-induced ADA.

If appropriate, data will be provided for:

- Pre-existing antibodies: ADA-positive subjects as a percentage of the total number of subjects, titer range (median and interquartile range (IQR)), percentage of treatment-boosted ADA-positive subjects, and duration of only pre-ADA, i.e., pre-ADA remained of same titer during the duration of study.
- Overall ADA prevalence: the number of ever-ADA-positive subject as portion of all study participants.
- Overall ADA incidence: combined results of treatment-boosted ADA-positive subjects and treatment-induced ADA-positive subjects (i.e., ADA-negative at baseline). For treatment-induced ADA incidence, peak positive titer and range (median, IQR). For treatment-boosted ADA, incl. the computed fold increase in titer (ratio of peak post-administration titer to baseline titer) and range of titer increases (median, IQR).
- Onset and duration of treatment-induced ADA. Regarding duration, a differentiation will be made between transient and persistent treatment-induced and boosted ADA.

Furthermore, the potential impact of ADA on PK, PD (as assessed by target engagement (TE)), clinical safety and efficacy will be explored descriptively for subjects with pre-existing or treatment-induced ADA.

- PK and PD: will be evaluated stepwise firstly looking into mean exposure for ADApositive vs. ADA-negative. In case any notable difference is found, PK will be considered by categorizing subjects into patients with impact of ADA vs. patients with no impact of ADA based on individual exposure over time to identify potential neutralizing/clearing ADA. To explore the ADA impact on PD, Safety and Efficacy the following analyses will be performed for ADA-positive vs. ADA-negative. Whether ADA is evaluated to have impact or not for an individual patients will be documented in patient listing.
- PD: TE as assessed by the plasma ratio of 'free' alpha-synuclein over 'total' alpha synuclein, plasma NfL, and MRI volumetric (as assessed by changes in primary regions)
- Safety: The number of hypersensitivity relevant TEAE's presented by SOC and PT, with focus on nature and timing of TEAE's (see below)
- Efficacy: Changes-from-baseline in UMSARS TS.

Nature of TEAEs

Consequences of immunogenicity on safety include the following TEAEs:

- Hypersensitivity reactions (as reported by Investigator)
- Hypersensitivity related TEAEs as Type I, II and III jointly, i.e., with a PT within 1) the SMQ of Hypersensitivity (narrow scope), 2) 'Cytokine release syndrome', and 3) the SMQ Vasculitis (narrow scope) or any of the 15 defined single PTs (see Appendix VI)

Timing of the TEAE

TEAE is only potentially related to immunogenicity if there is a temporal relationship to the ADA response, i.e., if there is a temporal relation between the onset of the TEAE and participants being or turning ADA positive, i.e., the participant is 'TEAE coincident ADA positive'.

All immunogenicity data will be listed by subject and period.

19 Blinded Data Reviews

A blinded data review will take place throughout the study to ongoing handle data issues. The reviews may include, but are not limited to, data quality, protocol adherence, and the appropriateness of design assumptions.

An independent Safety Data Monitoring Committee (DMC) will regularly monitor the patients' safety data according to the DMC Charter. The DMC will have access to unblinded information for the double-blind treatment for each patient. Members of the DMC will not be involved in other study-related tasks.

20 Interim Analyses

No interim analyses will be conducted for this study.

21 Sample Size Considerations

The 18331A sample size has been selected to ensure an appropriate power to detect a 40% slowing in MSA progression in the Lu AF82422 CO dose group compared to the placebo group on a 5% significance level evaluated 1-sided. Applying a repeated measures model with proportional treatment effect, yields an approximate 75% power when having N=60 patients allocated 2:1 in favour of Lu AF82422 treatment (i.e., 40 on Lu AF82422 *versus* 20 on

Study 18331A - Statistical Analysis Plan

placebo) when using the NLMIXED procedure for simulating in SAS[®]. To account for differences in treatment duration due to the study design, approximately 50% of the patients are expected to contribute with 60 weeks data and 25% of the patients with full 72 weeks data. On top, an overall 20% drop-out rate has been accounted for. For comparison, it is expected that the frequentist repeated measures model used for simulation is quite similar in relation to performance to the primary Bayesian repeated measures model.

22 Statistical Software

The statistical software used will be SAS[®], version 9.4 or later, and R, version 3.12 or later, respectively. For R, the packages Jags and Coda would be required to run the MCMC procedures.

23 Changes to Analyses Specified in the Protocol

• According to SAP section 16.1.4, TEAEs will be assigned to two periods rather than four periods as described in Protocol section 16.10.1, the reason being that the safety follow up periods following the DBP and the OLEP, respectively, will be part of the reporting periods rather than individual periods. In this way the first safety follow up period following the DBP will be reported as part of the DBP, and the safety follow up period following the OLEP will be reported as part of the OLEP.

24 Details on Data Handling

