# 4 Study Design

## 4.1 Overview of the Study Design

This study has been designed in accordance with the *Declaration of Helsinki*.

This is a phase II, interventional, randomized, double-blind, parallel-group, placebo-controlled, including an optional open-label extension (OLE), multi-centre study of the efficacy (slowing disease progression), safety, and tolerability of Lu AF82422 in patients with MSA. The efficacy of Lu AF82422 is assessed using the Unified Multiple System Atrophy Rating Scale Total Score (UMSARS TS); supportive assessments include evaluation of function, global impression of severity of illness, autonomic symptoms, disability, health-related quality of life, biofluid biomarkers, and imaging.

The study design is presented in Panel 1 and the scheduled study procedures and assessments for the DBP are summarized in Panel 2 and for OLE assessments are summarized in Panel 3.

This study will be conducted in compliance with the protocol, *Good Clinical Practice*, and applicable regulatory requirements.

60 patients, recruited from specialist centres, are planned for randomization: 40 patients in the Lu AF82422 group and 20 patients in the placebo group.

The target population for this study are patients with possible or probable MSA, as defined by the current consensus diagnostic criteria (see Appendix V). The study will recruit patients with evidence of parkinsonism (MSA-P) and/or cerebellar syndrome (MSA-C). Patients will be allowed stable treatment for managing their symptoms of MSA during the study.

In the DBP, patients will be randomized to Lu AF82422 or placebo (2:1) via a centralized randomization system (Interactive Response Technology [IRT]). To ensure a balanced treatment allocation, stratification will be applied according to two factors, that is, and Region (US/Japan, with a maximum of 25% of patients from Japan). Patients with a missing will be stratified to a separate group labelled "missing".

The study duration from the Screening Visit to the Safety Follow-up Visit is between 70 to 94 weeks for patients not entering the optional OLE period and between 166 to 190 weeks for patients continuing in the OLE. The study includes the following periods:

- Screening Period (4 weeks)
- Randomization Period (2 weeks)
- DBP (48 weeks up to 72 weeks)
- Optional OLE (96 weeks)
- Safety Follow-up Period (20 weeks after last IMP administration)

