## 7.4 Method of Assigning Patients to Treatment

IRT will be used in this study. Each patient will be assigned a screening number by the IRT, and that number will be used to identify the patient throughout the study. When a patient is to be randomized, the investigator or a designated, unblinded site staff will use the IRT. The IRT allocates the patient to a treatment group and assigns the patient a randomization number in accordance with the specifications from Biostatistics, Lundbeck.

Randomization will take place at Visit 2 after confirmation that the participant continues to meet the inclusion/exclusion criteria. Patients will be randomized 2:1 to receive either study drug or placebo.

In the optional OLE period, all patients will receive Lu AF82422.

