1.4 Exploratory Objectives

- To explore the target engagement of Lu AF82422 to α -synuclein
- To explore the target engagement of Lu AF82422 on pathological species of α-synuclein
- To explore the relationship between UMSARS, MRI parameters and NfL
- To explore the efficacy of Lu AF82422 for up to 72 weeks of treatment on clinical scales and biomarkers
- To collect patient experience with impaired functions due to MSA to support the interpretation of change on the UMSARS (Exit Interview subset)
- To collect patient experience with study participation (Study Experience Interview subset)

All during the Double-blind Period (DBP).

• To explore the effect of long-term treatment with Lu AF82422 during the open-label extension (OLE)

2 Study Design

- This is a phase II, interventional, randomized, double-blind, parallel-group, placebocontrolled, multi-centre study of the efficacy (slowing disease progression), safety, and tolerability of Lu AF82422 in patients with MSA. The efficacy of Lu AF82422 is assessed using the UMSARS TS; supportive assessments include evaluation of function, global impression of severity of illness, autonomic symptoms, disability, health-related quality of life, biofluid biomarkers, and imaging.
- The target population for this study is patients with possible or probable MSA, as defined by the 2008 Gilman diagnostic criteria. The study will recruit patients with evidence of parkinsonism (MSA-P) and/or cerebellar syndrome (MSA-C). Patients will be allowed stable treatment for managing their symptoms of MSA during the study.
- The patients [N=60] will be randomized to Lu AF82422 CCI or placebo (2:1) via a centralized randomization system (Interactive Response Technology [IRT]). Two strata variables will be applied to ensure a balanced treatment allocation of Lu AF82422 and placebo:CCI and Region (US/Japan, with a maximum of 25% of patients from Japan).
 - maximum of 25% of patients from Japan).
- The study duration from the Screening Visit to the Safety follow-up Visit is between 70 to 94 weeks for patients not entering the optional OLE period and between 118 to 142 weeks for patients continuing in the OLE. The study includes the following periods:
 - Screening period (4 weeks)
 - Randomization period (2 weeks)
 - Double-blind treatment period (48 weeks up to 72 weeks)
 - Optional OLE treatment period (48 weeks)
 - Safety Follow-up Period (20 weeks; will take place after last investigational medicinal product [IMP] administration)

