3.2 Definition of Periods

The study consists of the following periods:

- Screening Period (4 weeks): Screening Visit (V1) to Randomization Visit (V2)
- Randomization Period (2 weeks): Randomization Visit (V2) to Baseline DB Visit (V3)
- Double-blind Treatment Period (varying: 48 to 72 weeks): Baseline DB Visit (V3) to EoTDB Visit (V24) – Time point to be defined by IMP initiation on V3
- Optional Open-Label Treatment Period (48 weeks): from Baseline OLE Visit (V1E) to EoTOLE (V13E) - Time point to be defined by IMP initiation on V1E

Patients will subsequently after end IMP administration enter:

- Safety Follow-up Period 1 following DB (20 weeks): following the EoTDBP Visit (V24) to Safety Follow-up Visit (V25)
- Safety Follow-up Period 2 following OLE (20 weeks): following the EoTOLE Visit (V13E) to Safety Follow-up Visit (SFU-E)

Due to the late approval of the OLE protocol amendment some participants entering the OLE might have entered the first safety follow-up period prior to entering the OLE, and hence would have two safety follow-up periods.

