7.2 Withdrawals

The number of patients who withdrew from the study will be summarized by primary reason for withdrawal and all reasons for withdrawal by period.

If relevant, Kaplan-Meier failure plots of time to withdrawal will be presented by treatment group for the DB-Period. The time will be calculated from the date of first dose of IMP to the date of withdrawal in the DB-Period. Patients who completed the DB-Period according to their individual treatment duration (48-72 weeks) will be regarded as censored at the End of treatment visit.

Patients who withdrew from the study will be listed and the listing will include the number of days in the study until withdrawal, the number of days on IMP, the primary reason for withdrawal, and all reasons for withdrawal.

All tables, graphs, and listings will be based on the FAS.

8 Demographics and Baseline Characteristics

Demographics (sex, age, race, region), Screening MRI findings supporting MSA diagnosis and CCI ; baseline disease characteristics (incl. MSA sub-type, CSF/blood NfL level, result from the qualitative alpha-synuclein seeding assay (SAA), time since symptom onset and diagnosis); baseline physical examinations and baseline efficacy variables will be summarized by treatment group and overall. Concurrent as well as relevant past medical and psychiatric disorders will be coded using the *Medical Dictionary for Regulatory Activities* (MedDRA) and summarized.

A concurrent medical or psychiatric disorder is a disorder that is ongoing at the baseline Visit. A past medical or psychiatric disorder is a disorder that ended prior to the baseline Visit.

Demographics and baseline characteristics will be summarized based on the APTS, PKS and SBS, and baseline efficacy variables will be summarized based on the FAS.

9 Recent and Concomitant Medication

Recent and concomitant medication will be coded using the *WHO Drug Dictionary* (WHO-DDE).

Medications will be classified according to the start and stop time and summarized by anatomical therapeutic chemical (ATC) code, and generic drug name:

- medication discontinued prior to first dose of IMP
- concomitant medication continued after first dose of IMP
- concomitant medication started at or after first dose of IMP

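### SAP 16.9: time to death has no cut at the first open-label dose, so the comparison mixes placebo-controlled time with time after placebo patients who enter the OLE have switched to active drug

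*SAP*

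**What the plan says.** SAP 16.9 contains two things. The first is a table: "Events of deaths will be summarized by treatment group, reason of death and study period". The second is a time-to-event analysis: a Kaplan-Meier plot and, where applicable, a "Cox proportional-hazards model incl. treatment group" and the stratification factors. Living patients are "censored using the date of the last safety follow-up visit as last observed time point". The paragraph names no cut at the end-of-treatment visit of the double-blind period (EoTDBP) or at the first open-label dose, and it does not define treatment group.

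Four other places bear on how that rule works:

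- Protocol 7.4: "In the optional OLE period, all patients will receive Lu AF82422".
- SAP 3.2: some patients will have passed through the double-blind safety follow-up before entering the OLE and "hence would have two safety follow-up periods". For them, the last follow-up visit is the OLE one.
- SAP 7.2 limits the comparable withdrawal analysis: "Kaplan-Meier failure plots of time to withdrawal will be presented by treatment group for the DB-Period".
- SAP 16.1.4 ends the double-blind adverse-event phase at the first OLE dose, or at the double-blind safety follow-up for patients who do not enter the OLE.

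The OLE lasts 96 weeks in Protocol 4.1 and 48 weeks in SAP section 2.

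**The concern.** A hazard ratio for treatment group will be read as active drug against placebo. Once a placebo patient takes open-label drug, follow-up in that group no longer represents placebo. If the drug affects survival in either direction, the hazards in the two groups converge after crossover and the pooled hazard ratio moves towards 1. The risk is that a value near 1 is then taken as placebo-controlled reassurance on mortality, when much of the follow-up behind it was not placebo-controlled.

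The whole-study comparison is a legitimate analysis, but it answers a different question: early start against delayed start, which Protocol 4.2 names as an interest of the OLE. SAP 16.9 does not say which of the two questions its model addresses.

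**Working it through.** **1. Reproduce the stated durations.** Screening and randomisation take 4 + 2 = 6 weeks. The double-blind period (DBP) is 48-72 weeks. Safety follow-up is 20 weeks after the last dose, and the last dose falls 4 weeks before the end-of-treatment visit, so follow-up is 16 weeks after that visit (Protocol 9.5.1 and Panel 3, footnote b).

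Total = 6 + DBP + OLE + 16:

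- No OLE: 6 + 48 + 16 = 70 to 6 + 72 + 16 = 94 weeks
- 48-week OLE: 118 to 142 weeks, matching SAP section 2
- 96-week OLE: 166 to 190 weeks, matching Protocol 4.1

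**2. Share of follow-up after crossover.** This is for an OLE completer who enters on the day of EoTDBP, counted from baseline. Post-crossover time = OLE + 16.

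| OLE length | Post-crossover time | Total from baseline | Share |
|---|---|---|---|
| 48 weeks (SAP) | 64 weeks (about 1.2 years) | 112-136 weeks | 64/136 = 47% to 64/112 = 57% |
| 96 weeks (Protocol) | 112 weeks (about 2.1 years) | 160-184 weeks | 112/184 = 61% to 112/160 = 70% |

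**3. Effect on the hazard ratio.** The documents give no mortality rate, no expected mortality effect and no OLE uptake, so these are assumptions:

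- placebo death rate of 5%, 10% or 15% per year
- true hazard ratio of 0.50 or 0.70
- OLE uptake of 60%, 80% or 100%, unrelated to prognosis
- full drug effect immediately after crossover
- DBP lengths of 60 weeks for 50% and 72 weeks for 25% (Protocol 17.12), with the remaining 25% taken as 48 weeks
- no withdrawal other than death

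Death times for 400,000 patients allocated 2:1 were simulated with piecewise-constant hazards, and a Cox model was fitted by original arm. Ranges are over death rate and uptake.

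| True HR | Estimated HR, 48-week OLE | Estimated HR, 96-week OLE | OLE entrants censored at first open-label dose |
|---|---|---|---|
| 0.50 | 0.60-0.67 | 0.65-0.74 | 0.49-0.50 |
| 0.70 | 0.77-0.82 | 0.81-0.86 | 0.69-0.70 |

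A harmful effect (hazard ratio above 1) was not simulated. The same convergence of hazards applies to it, so the direction, towards 1, is the same.

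**4. Information available.** With d expected deaths among 60 patients, power = Φ(√(d × 2/3 × 1/3) × |ln HR| − 1.645), at one-sided 5%. That level is stated for the primary test; none is stated for mortality. One example has a 10% annual death rate, true HR 0.50, a 48-week OLE and 60% uptake:

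- As written: d = 6.8, HR 0.60. √(6.8 × 0.222) × 0.511 − 1.645 = −1.02, so power is about 15%.
- With the cut: d = 4.9, HR 0.50. √(4.9 × 0.222) × 0.693 − 1.645 = −0.92, so power is about 18%.

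Over all scenarios, expected deaths fall from about 4-18 to about 2-9, and power is 7-19% as written against 9-22% with the cut.

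**The case against.** The strongest reply is that the SAP's general rules already supply a double-blind version. SAP section 5 bases safety outputs on all treated patients for the double-blind period and on the OLE set for the extension. SAP 16.2 presents safety variables separately by period, and SAP section 23 folds the double-blind follow-up into the double-blind reporting period. SAP 16.9 also moves from the safety follow-up visit to the last such visit within one sentence. An analysis run at the double-blind database lock would contain less OLE time. The intended analysis may therefore stop where it should. That makes the wording ambiguous, but it does not settle it: 16.9 has its own censoring rule, which points to the last follow-up, and nothing there limits it to the DBP as SAP 7.2 does for withdrawals.

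Three stronger readings are tempting and are not supported.

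- *Every placebo patient ends up on active drug.* The OLE is optional (Protocol 4.1) and closed to anyone who withdrew in the DBP (OLE entry criteria, Protocol 6.3). The statement in Protocol 7.4 applies only within the OLE.
- *This is the only mortality comparison.* It is the only specified time-to-death model. Deaths are also tabulated by study period in 16.9, and the joint-rank sensitivity analysis in SAP 14.3.5 ranks patients on 48-week survival together with UMSARS, which OLE exposure cannot affect.
- *Two years of contaminated follow-up is a settled figure.* It needs the Protocol's OLE length. The SAP that contains the censoring rule gives about 1.2 years.

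Comparing by randomised arm is also an inference, though a reasonable one. The rule that keeps original placebo patients separate (SAP 14.2) is written for OLE efficacy data and is not repeated for deaths.

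A fair criticism of the obvious remedy also stands. If OLE entrants are censored at their first open-label dose while non-entrants are followed to the double-blind safety follow-up, the late risk set consists largely of patients who withdrew or declined. Because entry requires DBP completion, that censoring may be informative. The simulation took uptake as unrelated to prognosis and so does not test this.

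**Conclusion.** The point holds as a defect of specification with a predictable direction of bias. On its most natural reading, SAP 16.9 mixes placebo-controlled and post-crossover time, and for an OLE completer entering without delay about half or more of follow-up falls after crossover (47-57% or 61-70%, depending on which document's OLE length applies). Delayed entry or a delayed Visit 13E would change these shares. Under the assumptions listed, a true hazard ratio of 0.50 would appear as 0.60-0.74 and one of 0.70 as 0.77-0.86. If the drug has no effect on mortality, this mechanism introduces no bias.

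The consequence is small. The model is exploratory, is fitted only where applicable, lies outside the testing strategy, and covers 60 patients with few expected deaths. A reader might infer that a corrected analysis would give a useful answer on mortality. At 9-22% power under favourable assumptions it would not. The gain is an estimate whose meaning is clear.

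**What to change.** Add the following to SAP 16.9:

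1. Define the between-arm time-to-death analysis for the double-blind period, by randomised arm. OLE entrants are censored at the date of the first open-label dose, all other living patients at the double-blind safety follow-up. This is the cut that SAP 16.1.4 already uses for adverse events.
2. Add a version that cuts every patient at a common point, either EoTDBP or Week 48, to check whether OLE entry makes the censoring in item 1 informative.
3. State what treatment group means in this section.
4. Show whole-study survival by original arm separately, labelled as a supportive delayed-start comparison.
5. Reconcile the OLE length between the SAP and the Protocol.

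The cost is a few sentences and one or two extra outputs. The main comparison will contain fewer deaths (about 2-9 rather than 4-18 under the assumed rates). Under the same assumptions power is not reduced, because the hazard ratio is no longer diluted, but it remains very low.

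### The ADA impact comparison in SAP section 18 puts patients with unboosted pre-existing antibodies in the ADA-negative reference group, although the analysis is introduced for them

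*SAP*

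**What the plan says.** SAP section 18 sets its terms in Panel 4. An ADA-positive subject is "A subject with at least one treatment-induced or treatment-boosted ADA-positive sample at any time during the treatment or follow-up observation period". An ADA-negative subject is "A subject without a treatment-induced or treatment-boosted ADA-positive sample during the treatment or follow-up observation period". Boosting of pre-existing ADA requires that the "titer is greater than the baseline titer by a fourfold increase". Prevalence has its own row: "The proportion of subjects having anti-drug antibodies (including pre-existing antibodies) at any point in time". Incidence counts seroconversion or boosting.

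The output list in section 18 then has a prevalence item, "Overall ADA prevalence: the number of ever-ADA-positive subject as portion of all study participants", and a pre-existing item that begins "Pre-existing antibodies: ADA-positive subjects as a percentage of the total number of subjects". The pre-existing item goes on to ask for the boosted percentage and for the duration of pre-existing ADA that stayed at the same titer.

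The impact of ADA on PK, PD, safety and efficacy "will be explored descriptively for subjects with pre-existing or treatment-induced ADA". The PK part is stepwise. Mean exposure is compared between ADA-positive and ADA-negative first, and patients are sorted by their individual exposure only if a notable difference appears. For PD, safety and efficacy, "the following analyses will be performed for ADA-positive vs. ADA-negative". The safety display counts hypersensitivity-relevant TEAEs. Only patients who received Lu AF82422 are tested for ADA.

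**The concern.** The lead sentence of the impact analysis names patients with pre-existing ADA as part of the population of interest. The two-group split that follows uses Panel 4 terms, under which the unboosted patients among them are ADA-negative. They serve as the reference against which an antibody effect is judged.

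Two consequences follow. If unboosted pre-existing ADA alters exposure in the same direction as treatment-emergent ADA, including those patients in the reference group shrinks the mean-exposure difference. That difference decides whether the search for clearing or neutralizing ADA continues at patient level. Second, a hypersensitivity event in such a patient would be tabulated under ADA-negative, in the display meant to show whether antibodies and such events go together.

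**Working it through.** The plan states no ADA rate, so there is no figure to reproduce. The check compares the definitions as sets and then illustrates the size with assumed counts.

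**Notation.** N = active patients tested; k = patients with pre-existing ADA; b = those of the k who are boosted; t = treatment-induced cases. The protocol synopsis plans 40 patients on Lu AF82422, so N = 40 for the double-blind period. All 40 are assumed to be classifiable, with none ADA-inconclusive.

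**Classes under Panel 4.**
- ADA-positive subjects: b + t.
- ADA-negative subjects: N − (b + t), of whom k − b carry unboosted pre-existing ADA.
- Population named in the lead sentence of the impact analysis: k + t.

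The lead sentence and the comparison differ by exactly the k − b unboosted patients. Boosted patients are ADA-positive under both.

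**Share of the comparator that carries ADA** = (k − b) / (N − b − t), with assumed counts:
- k = 2, b = 0, t = 4: 2/36 = 5.6%.
- k = 4, b = 0, t = 4: 4/36 = 11.1%.
- k = 4, b = 1, t = 4: 3/35 = 8.6%.
- k = 0, or k = b: 0%.

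**Dilution of the exposure contrast.** Let the mean exposure be M0 with no ADA, Mp in ADA-positive patients and Mu in unboosted pre-existing patients, and let s be the share above. The reference mean as planned is (1 − s)·M0 + s·Mu. If unboosted ADA has the same effect as treatment-emergent ADA (Mu = Mp), the planned contrast is Mp − [(1 − s)·M0 + s·Mp] = (1 − s)(Mp − M0). With s = 4/36 the contrast is 32/36 = 89% of its undiluted value. If unboosted ADA has no effect on exposure (Mu = M0), nothing is lost.

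**Prevalence wording.** By Panel 4's prevalence row the numerator is k + t. If the ADA-positive subject term were used instead, it would be b + t, which is also the incidence numerator. The gap is (k − b)/40, or 1/40 = 2.5 percentage points per unboosted patient. With k = 4, b = 0, t = 4 the two results are 8/40 = 20% and 4/40 = 10%. With k = 4, b = 1, t = 4 they are 8/40 = 20% and 5/40 = 12.5%.

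**The case against.** Grouping patients by treatment-emergent response is a legitimate choice, and Panel 4 defines it clearly. The impact analysis is descriptive, the outputs are conditional on being appropriate and meaningful, and no test or decision on efficacy depends on them. The SAP also has safeguards. Individual ADA impact is to be recorded in a patient listing, all immunogenicity data are listed by subject and period, and the rule on the timing of TEAEs covers participants who already are ADA positive as well as those who become so.

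This limits the consequence but does not remove the conflict. The lead sentence still names patients whom the comparison places in the reference group. Listings do not change the tabulated contrast, and the individual exposure step is taken only if that contrast looks notable.

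Three stronger readings are tempting, and the documents do not support them.
- *Prevalence as planned equals incidence.* Panel 4's own prevalence row includes pre-existing antibodies, and the output item says ever-ADA-positive, which is not the defined subject term. Equality holds only if an analyst substitutes that term.
- *The pre-existing rate will be wrong.* Under the Panel 4 subject term, the boosted percentage in that item would be 100% by construction and the item on unchanged titer would have no patients. The item makes sense only if ADA-positive there means positive at baseline, and an analyst would read it so.
- *All patients with pre-existing antibodies count as ADA-negative.* Boosted patients are ADA-positive. Only unboosted ones are affected.

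The stated safety endpoint is also not damaged: it is the development of ADA, which incidence measures, and incidence is defined consistently.

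**Conclusion.** The point holds for the impact comparison. Section 18 includes unboosted pre-existing cases in the population of interest and then places them in the ADA-negative reference group. This can weaken the exposure contrast that gates the individual PK review, and it files any hypersensitivity events in these patients under ADA-negative. The prevalence and pre-existing items need only a wording alignment.

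The size depends on counts that the documents do not give. With 40 active patients and 4 treatment-induced cases, 2 to 4 unboosted pre-existing cases would make up 5.6% to 11.1% of the comparator. The exposure contrast would shrink by that share only if unboosted ADA acted like treatment-emergent ADA, which is an assumption. With no unboosted cases there is no effect. The analyses concerned are descriptive, and the primary and key secondary analyses are not touched.

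**What to change.** In SAP section 18:
1. Keep the Panel 4 ADA-positive subject term for incidence.
2. Show the PK, target engagement, safety and efficacy impact summaries in three groups: no ADA at any time; pre-existing unboosted ADA; treatment-induced or boosted ADA. At a minimum, take unboosted pre-existing cases out of the reference group, and state this for the mean-exposure step.
3. As wording alignment, state that ever-ADA-positive in the prevalence output follows Panel 4's prevalence row, and that ADA-positive in the pre-existing item means positive at baseline.

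The cost is SAP wording and one extra display group, which may be very small and hard to interpret by itself. Baseline ADA sampling is already in the protocol schedule (Panel 2), so no new samples are needed. The change should be made before ADA status is classified.
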